19.9 Interim analysis and criteria for the premature termination of the trial

An interim analysis will be performed after recruitment of the first 52 patients. The analysis will be limited to an analysis of safety data between the two groups. Provided there are no issues regarding safety or toxicity, the study will be continued with an increased dose in the intervention arm.

At the interim analysis, a qualitative assessment of all recorded AEs and SAEs will be undertaken by the DMC to determine if the trial should be discontinued on account of safety concerns. AEs will be coded by system organ class (SOC) and preferred term (PT), using MedDRA. An overview of all AEs, SAEs, relationship to IMP, intensity and AEs leading to withdrawals or death will be presented by treatment group. AEs will be summarised using descriptive statistics. Treatment emergent AEs will be analysed separately.

The number and percentage of subjects with abnormal vital signs and/or laboratory values will be presented by treatment group. The data may also be presented as shift tables (normal, abnormal and not clinically significant, abnormal and clinically significant) with screening values as a reference.

The trial will be terminated following the interim analysis based on the safety data. The criteria for termination (e.g. total SAEs per group) shall be defined by the DMC. Outside the planned interim analysis the study will be terminated only on the grounds of new safety concerns or unforeseen recruitment issues.

The sponsor retains the right to stop the study, should the need arise.

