11.6 Trial Design

This is a single-centre, randomized, placebo-controlled, parallel group study with a sequential groupdosing regimen (adaptive design). Its aim is to evaluate the safety and efficacy of Artesunate treatment compared to placebo, in addition to standard treatment, in severely injured trauma patients with traumatic hemorrhage. All subjects will be managed in accordance with local guidelines for traumatic hemorrhage.

Subjects will be assessed for eligibility upon arrival to the hospital. Due to the urgent/emergency nature of the intervention subjects will be recruited within 4 hours of their injury and within 2 hours of admission to the accident and emergency department. Eligible patients therefore need to be consented very soon after admission. As most, but potentially not all, subjects will be incapacitated at time of eligibility, consent can be obtained from relatives or if no relatives are present two

doctors (one independent of the trial) will decide on consent. If and when the subject regains physical and mental capacity they will be provided written information on the trial and will be given the opportunity to ask questions, informed consent will be sought for continuation in the trial. For any subject included but did not regain full capacity, consent will be sought from a relative or other appropriate representative for continuation in the trial.

Subjects will be randomized to one of three groups:

- Placebo arm (n = 35)
- Low Dose intervention arm: active drug 2.4mg/kg (n=35)
- High Dose intervention arm: active drug 4.8mg/kg (n=35)

The trial will be divided into two stages. The first stage will enroll patients into the Placebo (n=17) and Low Dose intervention arms (n=35), following which an interim analysis will be performed. The analysis will be limited to an analysis of safety data between the two groups. Provided there are no issues regarding safety or toxicity, the study will continue with the second phase enrolling patients into the high dose intervention arm (n=35) or placebo (n=18).

Each subject will be dosed and then remain in the study for 28 days or until they are discharged. There will be a 90-day follow-up though this will be conducted using data obtained via the NHS spine services (Health and Social Care Information Centre).

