13.6 Blinding

The trial participant, clinical team providing treatment (including pharmacy), and research investigators will be blinded to treatment group allocation. In addition, outcome assessors and data monitoring committees will also remain blind to group allocation.

However, due to the slight difference in opalescence of the IMP solution and placebo, and the requirement to visualise the IMP to confirm adequate re-constitution (see Section 15.12), it is not possible to blind the IMP administrator. Therefore, the IMP administrator, who will prepare the active ingredient IMP or placebo (diluent only), will be un-blinded.

In order to maintain blinding of the subject and clinical team, the IMP and placebo will be prepared in a separate room to the clinical team (Section 15.12). The administrator will simulate the time taken to re-constitute the IMP (6 minutes) when preparing the placebo, and administer it in a similar manner (i.e. as an intravenous injection over 1-2 minutes, given within the specified time-frame of one hour).

In order to maintain blinding of research investigators collecting follow-up data, a rota will be drawn up such that the investigator who administered the IMP/placebo will not be involved in collecting follow-up information for that subject. Our centre and its research team operate to a rota that has successfully conducted such clinical trial protocols previously.

Final unblinding of all trial participants will occur after creation of a locked analysis data set.

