19.3 Statistical analysis plan (SAP)

Full details of planned statistical summaries and analyses will be described in a separate Statistical Analysis Plan. Any deviations from the statistical analysis plan will be fully documented in the clinical study report, with the reasons for doing so. A brief summary of the SAP is provided below (see also Sections 19.4-19.13).

An interim analysis will be performed after recruitment of the first 52 patients. The analysis will be limited to an analysis of safety data between the two groups. Provided there are no issues regarding safety or toxicity, the study will be continued with an increased dose in the intervention arm.

The final analysis will be performed according to standard trial best-practice criteria. All data analysis will be performed before the breaking of the randomization code. Standard tests of two-group comparison will be used throughout. One- and two-way ANOVA will be used to analyse time-dependent (pKa) data. Safety data will be re-analysed with the final cohort as outlined for the interim analysis (see Section 19.9).

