28.0 Trial Committees

Trial Management Group

A Trial Management Group (TMG) comprising the Chief Investigator, Clinical Trials Coordinator and lead Clinical Research Fellow will be responsible for the day-to-day running and management of the trial. The Trial Management Group (TMG) will meet regularly to ensure all practical details of the trial are progressing and working well and everyone within the trial understands them.

Trial Steering Committee

The role of the Trial Steering Committee (TSC) is to provide overall supervision for the trial and provide advice through its independent chairperson. In accordance with the Trial Terms of Reference for the TSC, the TSC is responsible for periodically reviewing safety data and liaising with the DMC regarding safety issues. The ultimate decision on continuation or discontinuation of the trial lies with the TSC.

Members of the TSC will include membership from the TMG and independent members including:

Independent Chair Independent Lead Clinical Experts Lay-person/Patient Representative Clinical Trial Coordinator Co-optable Members including the trial chief investigator, trial statistician and trial collaborators

Data Monitoring (and ethics) Committee

In accordance with the Trial Terms of Reference for the DMC, the DMC are responsible for periodically reviewing un-blinded overall safety data to determine patterns and trends of events, or to identify safety issues, which would not be apparent on an individual case basis. The Regulations require that all Serious Adverse Events (SAEs), unless excluded in the protocol are reviewed by an appropriate Safety Monitoring Committee.

Members of the DMC will be completely independent from the running of the trial. For the purposes of this study, an independent member who can provide expert disease specific advice will join the core DMC.

The group will be called at the interim review for a formal analysis of safety data as outlined in Section 19 of this protocol. The TSG may also request further reviews by the DMC regarding any safety concerns or issues regarding trial management arising outside of the interim review period. The DMC may also provide advice to the Chair of the TSC and can recommend premature closure of the trial.

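### Section 13.6 blinds the DMC whose un-blinded reviews section 28.0 relies on, and the only safety review with fixed timing precedes all 4.8 mg/kg dosing

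*Protocol*

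**What the plan says.** The trial runs in two stages (Protocol 11.6). Stage 1 enrols 17 placebo and 35 low-dose (2.4 mg/kg) patients. Section 19.9 then provides: "An interim analysis will be performed after recruitment of the first 52 patients". That analysis compares safety between those two groups. If it raises no concern, "the study will continue with the second phase enrolling patients into the high dose intervention arm (n=35) or placebo (n=18".

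The next between-group safety analysis is in section 19.3: "Safety data will be re-analysed with the final cohort as outlined for the interim analysis (see Section 19.9".

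On stopping, the interim paragraph of 19.9 states: "The criteria for termination (e.g. total SAEs per group) shall be defined by the DMC". Outside the interim, 19.9 allows termination for new safety concerns or recruitment problems, and the sponsor may stop the study.

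On the DMC's access to data, two sections disagree:

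- Section 28.0: "the DMC are responsible for periodically reviewing un-blinded overall safety data to determine patterns and trends of events". It adds: "The TSG may also request further reviews by the DMC regarding any safety concerns".
- Section 13.6: "outcome assessors and data monitoring committees will also remain blind to group allocation".

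Section 13.6 also says that "research investigators will be blinded to treatment group allocation". Section 9.3 promises close monitoring of the higher dose for serious adverse events.

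**The concern.** Death, organ failure and infection are common in this population. An excess caused by the drug is hard to recognise from single cases, least of all by blinded staff. It shows in rates by arm against placebo patients enrolled over the same period.

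During stage 2, the protocol gives that task to one body, the DMC, through its periodic review. Section 28.0 assigns the review, gives no interval for it, and says the data are un-blinded. Section 13.6 says the committee is blind. A trial team or data manager who follows 13.6 would send the DMC data that cannot show the comparison. The lower dose would then have had a scheduled review by group, and the doubled dose none until everyone had been treated.

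At stake is whether harm at 4.8 mg/kg could be seen while there were still patients to protect. Prior risk is moderate. Section 9.1 reports that healthy volunteers tolerated up to 8 mg/kg, with no dose-related increase in adverse events except a fall in reticulocytes. It also says there are no human studies of artesunate for this use.

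**Working it through.** **1. Who is in the review with fixed timing (11.6, 19.9).**
Stage 1: 17 + 35 = 52, which matches the stated count. Stage 2: 35 + 18 = 53. Total: 52 + 53 = 105, as stated. High-dose patients in the 52-patient review: 0 of 35.

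**2. What could compare arms during stage 2.**

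| Mechanism | Section | Timing | By arm? |
|---|---|---|---|
| Interim analysis | 19.9 | after 52 patients | yes, low dose v placebo only |
| Periodic DMC review | 28.0, 13.6 | no interval stated | un-blinded in 28.0, blind in 13.6 |
| DMC review on request | 28.0, 13.6 | when requested | same conflict |
| Daily AE/SAE review | 11.6 | daily | case by case |
| Chief investigator's SAE review | 17.8 | within 24 hours of receipt | case by case; SUSARs assessed blinded (17.10) |
| Annual safety report | 18.0 | yearly | not described as by arm |
| Safety re-analysis | 19.3 | final cohort | yes, after all dosing |

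Only the DMC rows can give a comparison by arm before the end. Those are the rows that 13.6 contradicts.

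**3. How much of stage 2 a mid-stage look could still protect.**
Inputs: 105 patients in 24 months (19.2, even accrual assumed); 2:1 allocation (13.5.1); 28-day safety window (11.3.2).

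- Rate: 105 / 24 = 4.375 patients a month.
- Stage 2 length: 53 / 4.375 = 12.1 months.
- First 26 enrolled: 26 / 4.375 = 5.9 months. Split: 26 × 2/3 = 17.3 high dose and 8.7 placebo, so about 17 v 9.
- 28 days is 0.92 month, so their data are complete at 5.9 + 0.92, about 6.9 months.
- Enrolled meanwhile, with no pause: 0.92 × 4.375 = 4.0.
- Still to enrol: 53 − 26 − 4.0 = 23.0, of whom 23.0 × 2/3 = 15.3 are high dose.
- With 2 more weeks for tables and meeting, about 21.0 remain (14.0 high dose). With 4 more weeks, about 19.0 remain (12.6 high dose).

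**4. What a 17 v 9 look can show.**
Exact probability, from two independent binomials, that the observed high-dose rate exceeds the observed placebo rate by at least 20 points. The 20-point margin is illustrative. The 35% placebo rate borrows the mortality in 9.1 for patients given at least four red cell units. Lower rates are included because 12.2 excludes patients not expected to survive 48 hours.

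| Placebo rate | No effect | +10 points | +15 | +30 | +40 |
|---|---|---|---|---|---|
| 35% | 13.6% | 28.9% | 38.7% | 70.7% | 86.8% |
| 30% | 12.7% | 28.0% | 37.6% | 69.4% | 86.1% |
| 25% | 11.4% | 27.2% | 37.1% | 68.6% | 85.4% |
| 20% | 9.6% | 26.3% | 36.7% | 68.7% | 85.2% |
| 15% | 6.9% | 24.7% | 36.2% | 70.0% | 85.9% |

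A large excess would usually be visible. A modest one would usually not.

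**The case against.** The strongest reply is that section 28.0 already gives the DMC the function in question: aggregate, un-blinded review for patterns not visible in single cases, with no stage excluded. Further reviews can be requested, 19.9 permits stopping for new safety concerns at any time, and the DMC can recommend closure. The interval may be in the DMC's terms of reference or charter, which are mentioned but not shown. Most of this stands. A reader might infer that the high dose has no safety oversight, and the protocol does not support that. What the reply leaves unanswered is 13.6: the review in 28.0 can do its job only if the DMC sees data by arm, and 13.6 says it does not.

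One could reconcile the sections by supposing that the DMC sees arms under masked labels. That does not fit the wording of 28.0, and under 2:1 allocation the group sizes would largely give the labels away.

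A second tempting inference is that the events listed in 17.6 (deaths, infection, organ failure) would be missing from the safety tables. The documents do not show this. Section 17.6 itself calls them SAEs, 17.7 exempts them from 24-hour reporting only, and 19.9 has the DMC assess all recorded AEs and SAEs.

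It is also fair to say that the look has limited reach, as the last table shows, and that the 20-point margin and the 26-patient timing are choices made here.

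**Conclusion.** The point holds as a contradiction with a practical consequence. Section 13.6 blinds the committee that 28.0 expects to review un-blinded data, the only review with fixed timing covers 0 of 35 high-dose patients, and the next specified comparison by group comes after all dosing. Following 13.6 would defeat the one mechanism able to compare 4.8 mg/kg with concurrent placebo during stage 2, despite the promise in 9.3.

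A mid-stage review would come with about 19 to 23 patients (13 to 15 high-dose) still to enrol, assuming even accrual at the planned rate. It would show an observed 20-point excess in 69 to 71% of trials under a true 30-point excess, in 25 to 29% under 10 points, and in 7 to 14% under no effect, over assumed placebo rates of 15 to 35%. That is useful to a DMC exercising judgement, but too weak for a formal rule. The correction to 13.6 is needed whatever the charter says. The need to fix a review time in the protocol depends on the charter not already doing so.

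**What to change.** - **13.6:** state that the DMC sees safety data by arm, in agreement with 28.0. Participants, the clinical team, follow-up investigators and outcome assessors stay blind.
- **19.9 and 28.0:** state that one of the DMC's periodic reviews takes place when about 26 of the 53 stage 2 patients have 28-day data, using the 19.9 safety tables by arm against concurrent placebo.
- **19.9:** state that DMC-defined termination criteria apply at that review too. The DMC chooses events and thresholds, and the general ground of new safety concerns stays.
- If the charter already sets such a review, a cross-reference in 19.9 is enough, together with the correction to 13.6.

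Cost: one more meeting of the existing DMC on tables already planned, and a short amendment. If the amendment is classed as substantial, it goes to the MHRA and the ethics committee, with a response within 35 days (27.1). About 4 patients would be enrolled while the 28-day data mature, or 6 to 8 allowing 2 to 4 weeks for the meeting, unless enrolment pauses for a similar time. The DMC must also be ready for a 7 to 14% chance of a 20-point imbalance with no true effect. No efficacy data are examined, so the type I error of the primary analysis is unaffected.

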19.10 Subject population

The analysis populations will be defined as follows:

Intent-to-Treat (ITT) Population

The ITT population is defined as all patients randomised according to their treatment allocation irrespective of whether they received that treatment or not.

Per Protocol (PP) Population

Version 2.0 TOP-ART

The PP population is defined as all patients randomised and treated according to the protocol i.e. based on treatment that patients actually received. The primary efficacy analysis will be performed on this study population.

Safety Population

The safety population is defined as all patients randomised who received any partial dose of IMP and will be analysed based on treatment that patients actually received.

19.11 Procedure(s) to account for missing or spurious data

The study team will follow participants daily in order to maximise capture of follow-up data. Missing outcome data will be imputed where appropriate. Reasons for missing data will be recorded on the CRF during data capture where possible (e.g. observation not performed, sample not taken).

19.12 Other statistical considerations.

Any deviations from the original statistical plan will be reported in the clinical study report with reasons for doing so. Participants who withdraw from the study will be replaced. Evaluable patients are defined as those who meet study inclusion and exclusion criteria, provide consent for participation, are randomised to either treatment or comparator group and treated according to protocol, and reach the primary endpoint (SOFA score at 48 hours). Evaluable patients will analysed in the 'per protocol' analysis for comparison against the intention-to-treat analysis.

20.0 Data Handling & Record Keeping

20.1 Confidentiality

The Principal Investigator has a responsibility to ensure that participant anonymity is protected and maintained. They must also ensure that their identities are protected from any unauthorised parties. Information with regards to study participants will be kept confidential and managed in accordance with the Data Protection Act, NHS Caldicott Guardian, The Research Governance Framework for Health and Social Care and Research Ethics Committee Approval. All trial data will be stored in line with the Medicines for Human Use (Clinical Trials) Amended Regulations 2006 and the Data Protection Act and archived in line with the Medicines for Human Use (Clinical Trials) and all subsequent amendments as defined in the JRMO SOP 20 Archiving.

The Chief Investigator and the study team will adhere to these parameters to ensure that the Participant's identity is protected at every stage of their participation within the study. To ensure this is done accordingly, at time of consent each participant will be allocated a unique screening number by either the PI or a member of the study team before undergoing any screening procedures.

The subject's initials (the first letter of their first name and the first letter of their last name) will be used as a means of pseudo-anoymising parameters. This information will be kept on a screening log, and updated accordingly throughout the study. Once the patient has completed screening procedures and is enrolled onto the study, they will be allocated a unique study ID/randomisation number by the investigator.

Subject identifiable information (name, date of birth, hospital number) will be recorded for the purposes of consent (on the consent log) and data collection including AEs and SAEs (hardcopy Case Report Form). In addition, contact information for the subject (address, telephone number and General Practitioner Details) will be recorded in the consent log in the event an investigator may need to contact the subject or their GP with regards to the trial. Access to all identifiable information will be limited to the study investigators.

If any subject information needs to be sent to a third party (including correspondence/ communication to central laboratories, CROs, sponsor) the PI and the study team will adhere to patient pseudo-anonymous parameters. This includes the patient initials, date of birth, gender as well as the unique study ID/randomisation number. Any information that is to be collected by these third parties will utilise these coded details for any relevant documents as well as maintaining databases.

As Investigator, you agree that all information communicated to you by the sponsor is the exclusive property of the sponsor and you will ensure that the same shall be kept strictly confidential by you or any other person connected with the work and shall not be disclosed by you or such person to any third party without the prior written consent of the sponsor. You shall communicate the results of the work promptly to the sponsor.

All rights and interests worldwide in any inventions, know-how or other intellectual or industrial property rights which arise during the course of and/or as a result of the clinical study which is the subject of the protocol or which otherwise arise from the information or materials supplied under this agreement, shall be assigned to, vest in and remain the property of the sponsor.

All investigators and trial site staff must comply with the requirements of the Data Protection Act 1998 with regards to the collection, storage, processing and disclosure of personal information and will uphold the Act's core principles.

20.2 Data Custodian Details

The Chief Investigator [name], is the 'Custodian' of the data research data (Address: Centre for Neuroscience and Trauma, Blizard Institute, Barts & The London School of Medicine & Dentistry, Queen Mary University of London, [name]. [contact]. Email: [contact]). Barts Health NHS Trust and Queen Mary University of London policy is that study data should be kept for 20 years following completion of the study.

Subject identifiable information (name, date of birth, hospital number) will be recorded for the purposes of consent and data collection including AEs and SAEs (hardcopy Case Report Form) which will be stored in a secured locked room on site, accessible only to members of the study team. This data will also be stored in a secure, electronic password protected consent log stored on the Barts Health NHS Trust server, along with contact information for the subject (address, telephone number and General Practitioner Details) in the event an investigator may need to contact the subject or their GP with regards to the trial. Access to all identifiable information will be limited to the study investigators.

If any subject information needs to be sent to a third party (including correspondence/ communication to central laboratories, CROs, sponsor) the PI and the study team will adhere to patient pseudo-anonymous parameters. This includes the patient initials, date of birth, gender as well as the unique study ID/randomisation number. Any information that is to be collected by these third parties will utilise these coded details for any relevant documents as well as maintaining databases.

Participants will be anonymised with regards to any future publications relating to this study.

